## 9.3. *Maintenance and Calibration of Equipment*

Equipment will be monitored regularly for maintenance and calibration as per relevant company and product manuals.

## 10. TREATMENT OF PARTICIPANTS

### 10.1. Administration of Study Product

Participants will be instructed to take one capsule by mouth with meals, three times daily for 40 days, and then two times daily for the remainder of the study, as per the manufacturer's recommended guidelines.

### 10.2. Study Product Storage and Accountability

#### 10.2.1. Storage Requirements

Study product is to be stored at room temperature in a secure storeroom/cupboard. The storage facility should be kept locked to prevent unauthorised access and to ensure accountability of the study product at all times.

#### 10.2.2. Accountability

A Product Tracking spreadsheet is used for keeping track of who, where and when study product have been issued or dispensed to.

- **Receipt of Study Product:** Once invoice has been checked, the study product will be entered into the Study Product Tracking spreadsheet.
- **Issue of Study Product to Clinical Trial Participants:** The Optometrist is responsible for documenting the dispensing of the study product on the participant case record form.
- **Disposal of Unused Supplies:** Instruction will be obtained from the sponsor as to how to handle returned, unused study product.

### 10.3. Concomitant Therapy

Whilst participating in this clinical trial participants are not permitted to enrol in other clinical trials.

Participants must not use or have a need for any systemic or topical medications which may alter normal ocular findings/are known to affect a participant's ocular health/physiology either in an adverse manner or risk providing a false positive.

## 10.4. Participant Instructions

### General instructions to all participants

- Contact the clinic immediately if problems are experienced or if they have any questions or concerns
- Ingest the study product daily as per manufacturer's recommendation
- Return the unused study product at each follow-up visit
- Store the study product at room temperature and keep out of reach of children
- Continue to use any artificial tear supplements at the same frequency throughout the study, as used prior to the study
- Do not make any substantial changes to your intake of fish/diet for the duration of the study, unless instructed to do so for health/medical reasons. If so, please advise the study investigator as soon as possible.

## 11. ASSESSMENT OF EFFICACY

### 11.1. Parameters

- Ocular comfort
- Product usage
- Visual acuity
- History
- Tear lipid layer thickness
- Tear evaporation rate
- Non-invasive tear break-up time
- Tear meniscus height
- Tear volume (phenol red thread test)
- Eyelids: redness and swelling
- Bulbar conjunctival redness
- Corneal and conjunctival staining
- Body mass index
- Body fat composition

### 11.2. Methods

Ocular comfort and product usage will be assessed by completion of a paper questionnaire (Appendix II).

History (including medical and general health) will be recorded on the Participant History File at all visits.

Habitual visual acuity will be measured at each visit using standard letter charts.

Tear lipid layer thickness will be measured using the LipiView Ocular Surface

Interferometer. The participant's eye is positioned in front of an illumination source that is directed toward the tear film on the corneal surface. The camera records a 20-second video of the tear film interference and subsequently displays a value in interferometric colour units (ICU), where 1 ICU approximates 1nm of lipid layer thickness.

A photograph of the anterior eye will be taken at the Baseline visit for participants who are eligible to be randomised into the study. From the photograph, ocular surface area will be measured in order to calculate the absolute tear evaporation rate.

Tear evaporation rate will be measured using the Vapometer. To minimize the effect of skin evaporation, petroleum jelly (Vaseline\_, <http://www.unilever.com.au/brands-in-action/detail/Vaseline/299339/>) will be applied over the upper eyelid and the surrounding areas. Three measurements will be taken for each eye under open eye and closed eye conditions. Each measurement will be recorded and the absolute evaporation rate will be calculated for each eye.

Non-invasive tear break-up time will be measured using the Oculus Keratograph 5M. The participant's eye is positioned in front of a placido disc illumination which allows detection of the tear film. Participants will be asked to blink three times and then to hold their eyes open for as long as possible, or until instructed to blink again by the study investigator. Three consecutive measurements of non-invasive tear break-up time will be recorded for each eye.

Tear meniscus height will be measured using the Oculus Keratograph 5M. The participant's eye is positioned in front of a placido disc illumination which allows detection of the tear film. Participants will be asked to blink once and an image of the tear prism will be captured immediately after the blink. Tear meniscus height will be obtained using the measuring guide software.

Tear volume will be measured using the phenol red thread test. The folded 3mm end of the thread is placed at a point approximately 1/3 of the distance from the lateral canthus of the lower eyelid with the eye in primary position. Participants are instructed to look straight ahead and blink normally during the test. When 15 seconds have elapsed, the thread is gently removed and the entire length of the red portion of the thread is measured in millimetres from the very tip, regardless of the fold.

Slit lamp biomicroscopy will be performed at each visit. This will be used to assess the following variables and rated using the CCLRU (Appendix III) and CIBA Grading Scales (Appendix IV).

- Eyelids: redness and swelling
- Bulbar conjunctival redness

- Corneal and conjunctival staining

Body mass index and body fat composition will be measured at the first visit only. To calculate body mass index ( $\text{weight}/\text{height}^2$ ), participants will be asked to stand on a digital scale (Charder Scale MS 3400; Charder Electronic Co. Ltd., Taichung City, Taiwan) whereby weight and height will be measured. Body fat composition will be measured using a Tanita monitor (Tanita BC-601, Tanita, Australia). Participants will be asked to stand on the Tanita monitor, which sends a very low, safe electrical signal from four metal electrodes through the participant's feet, and uses bioelectrical impedance analysis to calculate body fat composition.

## 12. ASSESSMENT OF SAFETY

### 12.1. Parameters

- Discomfort
- History
- Visual acuity
- Ocular redness: bulbar conjunctiva
- Corneal and conjunctival staining
- Health and wellbeing questionnaire

### 12.3. Definitions

#### 12.3.1. Adverse Events

**Adverse Event:** Any undesirable clinical occurrence in a participant, whether it is considered to be device-related or not, that includes a clinical sign, symptom or condition and/or observation of an unintended technical performance or performance outcome of the device.

Adverse Events may be classified as Serious, Significant, Non-significant or Unanticipated as defined further on.

### **12.3.2. Serious Adverse Events**

Any adverse medical occurrence that:

- led to death.
- led to a serious deterioration in health of a Participant user or other.  
This would include:
  - a life threatening illness or injury.
  - a permanent impairment of body function or permanent damage to a body structure.
  - a condition requiring hospitalisation or increased length of existing hospitalisation.
  - a condition requiring unnecessary medical or surgical intervention.
  - foetal distress, foetal death or a congenital abnormality/birth defect.
- might have led to death or a serious deterioration in health had suitable action or intervention not taken place. This includes:
  - a malfunction of a device such that it has to be modified or temporarily/permanently taken out of service.
  - a factor (a deterioration in characteristics or performance) found on examination of the device.

### **12.4. Reporting**

In the event of persistent irritation, redness, reduced visual acuity or any other unusual signs or symptoms, the participants will be advised to remove their lenses immediately and contact the clinic.

Non-serious and anticipated device-related adverse events and adverse events should be recorded as part of Good Clinical Practice. Sponsors are expected to maintain up-to-date tabulations and/or line listings of all adverse device events.

All Serious Adverse Events should be reported within 24 hours to the HREC as per their reporting requirements. This should be followed by a more detailed written report commenting on potential confounding factors, results of investigations, treatment required and outcome. The Co-sponsor and the Principal Investigator should review the events in conjunction with the known information about the device, and make a determination as to whether the event is device-related or not.

All adverse events should be reported to the Co-sponsor no later than 10 days after the event.

### 12.4.1. Foreseeable Adverse Events

Risks associated with the use of the study product are likely to be gastric/digestive in nature and may include:

- Stomach pain (<2%)
- Diarrhoea (<1%)

Potential risks associated with the study procedures include:

- Eye irritation/discomfort (less than 1 in 20 chance)
- Watery eyes (less than 1 in 100 chance)

### 12.4.2. Other Observations

There may be other situations that may necessitate rapid communication to regulatory authorities. Scientific and medical judgment should be applied for each situation. In general, information that might materially influence the benefit-risk assessment of a product or that would be sufficient to consider changes in product administration or in the overall conduct of a clinical investigation represent such situations.

## 12.5. Follow-up

Participants who experience an adverse response during the course of the trial will be followed up until the condition resolves or the participant is referred to another practitioner. **Permanent discontinuation:** will occur when, in the optometrist's opinion (or ophthalmologist's, if participant has been referred), continued use of the study product will be detrimental to ocular or general health.

## 12.6. Referrals

Participants will be referred to a medical expert when judged by the optometrist to be necessary. After hours, participants will be referred to Sydney Eye Hospital.

## 13. STATISTICS

### 13.1. Description

Data stored in relational databases will be imported into SPSS software for statistical purposes. Statistical analysis will initially be reported in Excel. The study may employ at least one interim analysis. Data will be investigated for quality using range checks and frequency distribution. Underlying distributions of variables will be tested. In general, variables measured on an interval scale with a sufficiently large sample size will be considered to follow a normal distribution. Details of statistical analysis are described in Section 13.1.3.

#### 13.1.1. Number of Participants

138 participants will be recruited (69 in each group, which includes allowance for a 10% drop-out rate).

This sample size was calculated on the basis of detecting a difference in OSDI score of 10, with a standard deviation of 20, assuming an estimate of type 1 error  $\alpha = 0.05$  and power of 80% for a two tailed test. These values were obtained from Schiffman et. al. who demonstrated a mean difference in OSDI score of 10 between normal subjects and those with mild to moderate dry eye, with a standard deviation of up to 20.

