# 1. PROTOCOL SYNOPSIS

Table 1

Protocol Title	The effects of dietary supplementation with a combination of flaxseed oil, borage oil and fish oil omega-3 fatty acids on ocular comfort including symptoms of dry eye.	
Protocol ID Number	SOVS2016-045	
Trial Classification	Evaluation	
Investigator(s)/Site(s)	Eye Research Group @ SOVS The University of New South Wales Sydney, Australia	
Overall Duration of Trial	1 year	
Number of Trial Participants Planned	138	
Planned Start Date	February 2017	
Primary Objective	To investigate the efficacy of a nutraceutical formulation (combination of flaxseed oil, borage oil and fish oil omega-3 fatty acids) on ocular symptoms including dry eye, compared to a placebo control.	
Secondary Objective	To evaluate the safety of a nutraceutical formulation (combination of flaxseed oil, borage oil and fish oil omega-3 fatty acids) over a 3 month period.	
Primary Safety Variable(s)	Visual acuity Biomicroscopy: ocular redness, corneal and conjunctival staining	
Primary Efficacy/Performance Variable	Subjective symptom scores measured using OSDI, OCI and DEQ-5	
Experimental design	 Retrospective  Prospective  Single group  Multiple group  Parallel group  Cross over  Contralateral	 Single masked (Trial Participant)  Single masked (Investigator)  Double masked  Sponsor masked  Open label  Other

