### 6.1.3. Clinical Trial Population

A total of 138 participants will be recruited for the study, which includes allowance for a 10% drop-out rate).

This sample size was calculated on the basis of detecting a difference in Ocular Surface Disease Index (OSDI) score of 10, with a standard deviation of 20, assuming an estimate of type 1 error  $\alpha = 0.05$  and power of 80% for a two tailed test. These values were obtained from Schiffman et. al. who demonstrated a mean difference in OSDI score of 10 between normal subjects and those with mild to moderate dry eye, with a standard deviation of up to 20.

Every effort will be made to stratify enrolment by disease severity to ensure participants with mild, moderate and severe dry eye are represented in the study population. Stratification will be in a 2:2:1 fashion i.e. OSDI score >12 (55 participants), OSDI score >20 (55 participants) and OSDI score >45 (28 participants).

Trial participants will be recruited from the local population at the investigational site. An e-mail invitation will be circulated to all SOVS staff, the Brien Holden Vision Institute, the Centre for Eye Health, SOVS post-graduate students, UNSW administrative staff and previous study participants who have indicated their willingness to be contacted to participate in future research studies. Advertisements may also be posted in University newsletters, notice boards, websites, local newspapers, social media (e.g. Facebook), on the SOVS clinic TV screen and other local advertising and community websites.

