#### 13.1.2. Significance

A p-value less than or equal to 5% will be considered to be statistically significant.

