#### 13.1.3. Analysis

Participants who have commenced the study treatment will be included in the analysis dataset. Reasons and frequency distribution of participants discontinued at Baseline will be reported. The analysis of efficacy variables such as subjective ratings will employ only scheduled and evaluable visits.

The analysis of safety variables such as adverse responses will include all visits, including all unscheduled visits.

Data will be summarised as means  $\pm$  standard deviations for variables measured on an interval scale and median  $\pm$  inter-quartile range for ordinal variables. Statistical tests will be employed to determine significant differences between between visits and  $p \leq 0.05$  will be considered statistically significant. Multiple comparisons will be adjusted using Bonferroni's correction. Commonly used tests of significance at each visit may include paired t-tests and group t-test for parametric data and Wilcoxon sign rank test and rank sum test for non-parametric data or repeated measures Analysis of Variance (ANOVA) for parametric data to determine differences between within-subject factors. Ranked variables will be analysed non-parametrically using Friedman's analysis of variance or Wilcoxon Signed Rank test to determine differences. Paired categorical variables will be compared using McNemar's test and grouped categorical variables will be analysed using Chi-Square tests.

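### The sample size supports about 80% power for one OSDI test at 0.05, but three questionnaires are named as primary and the Bonferroni family is undefined

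*Combined protocol and SAP*

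**What the plan says.** Section 13.1.1 gives the sample size: "138 participants will be recruited (69 in each group, which includes allowance for a 10% drop-out rate". It rests on "detecting a difference in OSDI score of 10, with a standard deviation of 20", with a type 1 error of 0.05 and "power of 80% for a two tailed test". Section 6.1.3 repeats the total and the inputs: "A total of 138 participants will be recruited for the study, which includes allowance for a 10% drop-out rate". Neither section mentions OCI or DEQ-5, or any division of alpha.

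The Synopsis (section 1) is broader. Its primary efficacy variable is "Subjective symptom scores measured using OSDI, OCI and DEQ-5". Section 6.1.6, the primary endpoint, speaks of questionnaires in the plural and identifies no instrument and no visit.

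On significance, section 13.1.2 sets one threshold: "A p-value less than or equal to 5% will be considered to be statistically significant". Section 13.1.3 then adds: "Multiple comparisons will be adjusted using Bonferroni's correction". It does not say which comparisons form the family. The sentence just before it concerns differences between visits, and the sentence after it lists tests that may be used at each visit.

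**The concern.** The power statement describes one test, while the endpoint definition describes three. A reader of the final report could not tell from the plan whether OSDI was to be judged at 0.05 or at 0.0167, whether success on any one questionnaire would count, or which visit carries the claim.

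Either the stated 80% does not describe the test that is performed, or three primary tests share no control of the type 1 error. In both cases the choice of instrument, visit and threshold stays open until results are seen.

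**Working it through.** **Inputs.** Difference 10, SD 20, two-sided alpha 0.05, power 80%, 69 per arm, 10% drop-out (all section 13.1.1). Three primary questionnaires (section 1). Bonferroni with no stated family (section 13.1.3).

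**Step 1: the plan's own figure.** With the normal approximation,

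n per arm = 2 × SD² × (1.960 + 0.842)² / difference² = 2 × 400 × 7.849 / 100 = 62.8, so 63.

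The exact two-sample t-test needs 64. The stated 69 matches 62.79 × 1.1 = 69.07; the plan does not show its inflation step, so this route is an inference. Dividing by 0.9 gives 63/0.9 = 70, or 64/0.9 = 71.1, so 72. The stated figure is reproduced to within 1 to 3 participants per arm.

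**Step 2: power after drop-out, one OSDI test at 0.05.** 69 × 0.9 = 62.1, so about 62 per arm. The expected test statistic is (10/20) × √(62/2) = 0.5 × 5.568 = 2.784.

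- Normal: Φ(2.784 − 1.960) = Φ(0.824) = 79.5%.
- Noncentral t: 78.9%.

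The drop-out that 69 per arm can absorb at 80% power is 1 − 63/69 = 8.7% (normal) or 1 − 64/69 = 7.2% (t).

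**Step 3: if Bonferroni covers the three questionnaires.** Alpha per test = 0.05/3 = 0.0167, critical value 2.394.

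- Normal, 62 per arm: Φ(2.784 − 2.394) = Φ(0.390) = 65.2%.
- Noncentral t, 62 per arm: 64.0%.
- With no drop-out at all (69 per arm): 70.6% (normal) or 69.6% (t), so drop-out is not what drives the gap.
- For 80% power on OSDI: 84 (normal) or 86 (t) evaluable per arm. After dividing by 0.9 and rounding up, that is 94 or 96 per arm recruited, 188 or 192 in total.

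**Step 4: if Bonferroni does not cover them.** Each questionnaire is tested at 0.05. Where success on any one counts, the chance of at least one false positive is 1 − 0.95³ = 14.3% if the tests are independent (an assumption). The upper bound whatever the correlation is 3 × 0.05 = 15%. Positively correlated scores would usually give less than the independent figure.

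**The case against.** Three arguments go the other way.

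**The arithmetic is sound.** A reader might infer from 62 per arm and 78.9% that the promised 80% is simply not delivered. The documents do not support that for a single OSDI test. The gap is about one point, and it comes from multiplying rather than dividing for drop-out and from normal versus t. Section 13.1.1 describes the SD as up to 20, an upper value; at SD 19.7 the t-test power with 62 per arm is 80.1%, and at SD 19 it is 82.8%. This objection stands. It does not rescue the Bonferroni case: at alpha 0.0167, 80% power with 62 per arm would need an SD of about 10 × 5.568 / (2.394 + 0.842) = 17.2 (normal), well below the planning value.

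**The Bonferroni sentence may not concern the questionnaires.** A reader might infer that the plan commits itself to testing OSDI at 0.0167. It does not say so. The sentence follows one about differences between visits, and a correction for between-visit comparisons is at least as natural a reading. This also stands, so the 64% is conditional. But that reading leaves the three primary questionnaires with no multiplicity rule, which is the other side of the same problem.

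**64% is not the power of the trial.** It is the power for OSDI alone. If success on any one of the three counts, power is at least that. How much higher cannot be computed, because the plan gives no effect, SD or correlation for OCI or DEQ-5. This stands too.

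**Conclusion.** The point holds as a mismatch between the powered test and the named primary endpoint. It does not hold as an error in the sample size arithmetic. The 138 participants give 78.9% to 79.5% power for a single between-group OSDI comparison at two-sided 0.05 with 62 per arm; the shortfall from 80% is minor.

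The plan does not say that this is the only primary test. Depending on a family that section 13.1.3 leaves undefined, either OSDI power falls to about 64% to 65%, which is 15 to 16 points below the stated figure, or three primary tests run unadjusted, with a family-wise error of about 14% under independence and 15% at most.

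The power figures assume the plan's own difference and SD and exactly 10% loss in each arm. The error figures assume that success on any one questionnaire counts, which the plan neither states nor rules out.

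**What to change.** **Preferred.** In the Synopsis and section 6.1.6, name the between-group comparison of OSDI at 3 months as the single primary test at two-sided 0.05, and list OCI and DEQ-5 as supportive or secondary. In sections 6.1.3 and 13.1.1, state that the power refers to that test and is about 79% to 80% with 62 per arm after 10% drop-out. In section 13.1.3, say which comparisons the Bonferroni correction covers.

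**Alternative.** Keep all three questionnaires as primary, define them as the Bonferroni family in section 13.1.3, and restate the OSDI power in sections 6.1.3 and 13.1.1 as about 64%.

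**Cost.** Neither route needs extra participants. The preferred route is more than an edit of wording: OCI and DEQ-5 lose primary status, so the endpoint hierarchy changes and the change falls under the amendment process of section 15.1.3. The alternative leaves a less favourable stated power; restoring 80% for OSDI under it would take about 188 to 192 participants. Whichever is chosen should be fixed before any comparison by group is seen.

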## **5. STUDY OBJECTIVES AND CLINICAL HYPOTHESIS**

### **5.1. Study Objective**

The objective of this study is to evaluate ocular symptoms and signs when consuming the supplement nutraceutical formulation (combination of flaxseed oil, borage oil and fish oil omega-3 fatty acids) daily over a 3 month period, compared to a placebo control.

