### **5.2. Clinical Hypothesis**

A greater reduction in ocular discomfort and/or signs of dry eye will be observed after daily consumption of the supplement nutraceutical formulation (combination of flaxseed oil, borage oil and fish oil omega-3 fatty acids) over a 3 month period compared to a placebo control.

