### 6.1.2. Randomisation and Masking

Prior to initiation of study treatment, each subject who provides informed consent will be assigned to a subject number that will serve as the subject identification number on all study documents. Subject numbers will be assigned in ascending order and should not be omitted or reused.

Eligible subjects will be stratified according to dry eye severity (mild, moderate or severe) and then randomly assigned to 1 of the 2 study treatments. A randomization scheme will be prepared in advance.

Test and placebo capsules will be manufactured in accordance with local regulations including the TGA guidelines. All capsules will be identical in appearance as the outer capsule will be the same as the commercial test product. The manufacturer will code, bottle and label the test and placebo capsules to ensure that participants and investigators will be masked throughout the study duration. Both test and placebo capsules will have the same outer packaging and will be labelled as capsule "A" or "B". The code will be broken after completion of the study and data analysis, or if required for participant safety.

The recommended dosage will be 3 capsules per day by mouth to be taken with a meal for 40 days, and then 2 capsules per day thereafter for approximately 50 days, as per the manufacturer's guidelines.

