### **6.1.6. Primary Endpoint**

Subjective ocular comfort and symptoms assessed using validated questionnaires.

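### The sample size describes one OSDI test at 0.05, but three questionnaires are listed as primary with no lead scale, visit, success rule or Bonferroni family, so the stated 80% power and 5% error are not tied to a defined primary test

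*Combined protocol and SAP*

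**What the plan says.** Section 13.1.1 (and 6.1.3, in almost the same terms) bases the sample size on one scale: "This sample size was calculated on the basis of detecting a difference in OSDI score of 10, with a standard deviation of 20", with two-sided alpha 0.05, 80% power, 69 per group and a 10% drop-out allowance.

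The synopsis gives the primary efficacy variable as "Subjective symptom scores measured using OSDI, OCI and DEQ-5", with no ranking. Section 6.1.6 gives the primary endpoint as "Subjective ocular comfort and symptoms assessed using validated questionnaires", with no scale, visit or summary measure.

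Section 13.1.3 leaves the test and the visit open: "Commonly used tests of significance at each visit may include paired t-tests and group t-test for parametric data". On multiplicity it says only "Multiple comparisons will be adjusted using" Bonferroni's correction, without naming the comparisons covered. Section 6.1.4 schedules two post-baseline visits, at 1 and 3 months. Section 13.1.2 applies a 5% threshold generally, and section 13.1 permits at least one interim analysis without allocating any alpha to it.

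The objective (5.1) is framed as "daily over a 3 month period, compared to a placebo control" and the hypothesis (5.2) as "over a 3 month period compared to a placebo control". Neither names an analysis visit.

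**The concern.** A power statement belongs to a specific test. Here the calculation describes one OSDI comparison, while the endpoint text could cover up to six between-arm questionnaire tests (three scales at two visits). The plan does not say whether one success is enough, whether all three scales must succeed, or whether OSDI leads.

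At stake is what a positive result would mean. If alpha is split across the scales, the 80% does not apply to OSDI. If it is not split and any scale may carry the claim, the 5% does not apply to the trial's conclusion. In both cases the headline scale and visit remain open until the data are analysed.

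**Working it through.** **Inputs from the documents.** Difference 10, SD 20, two-sided alpha 0.05, power 80%, 69 per arm, 10% drop-out (13.1.1); three scales (synopsis); two post-baseline visits (6.1.4). Evaluable per arm: 69 × 0.9 = 62.1, taken as 62.

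**Inputs assumed.** The documents give no correlations between the scales and no effects for OCI or DEQ-5. Correlations from 0 to 0.9 are shown. Where an effect is needed for the other scales, a standardised effect of 0.5 is used, the same as OSDI's 10/20.

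**1. Reproduce the plan's figure.** n per arm = 2 × (1.960 + 0.842)² × (20/10)² = 62.8, so 63, or 126 in total. Adding 10% gives 126 × 1.1 = 138.6; dividing by 0.9 gives 70 per arm, or 140. The stated 138 is therefore consistent with one unadjusted OSDI comparison. The calculation itself is not at fault. (The exact t-test needs 64 per arm.)

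**2. OSDI power if Bonferroni applies.** The noncentrality with 62 per arm is 10 / (20 × √(2/62)) = 2.784. Power from the noncentral t distribution at 0.05/k:

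| Family | k | Alpha per test | Power, 62 per arm | Power, 69 per arm |
|---|---|---|---|---|
| OSDI, one visit | 1 | 0.05 | 78.9% | 83.1% |
| OSDI, two visits | 2 | 0.025 | 69.6% | 74.8% |
| Three scales, one visit | 3 | 0.0167 | 64.0% | 69.6% |
| Three scales, two visits | 6 | 0.0083 | 54.2% | 60.3% |

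Section 13.1.1 describes the source SD as up to 20. At alpha 0.0167 with 62 per arm, power is 74.6% at SD 18 and 80.0% at SD 17.

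**3. Error if the scales are not adjusted and any one may succeed.** Under independence, 1 − 0.95³ = 14.3%. Simulating three equicorrelated two-sided tests at one visit gives 12.5% at correlation 0.5, 9.8% at 0.8 and about 8% at 0.9.

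**4. Any one of three, with Bonferroni.** Familywise error is 4.9% at correlation 0, falling to 3.0% at 0.9. With effect 0.5 on each scale, the chance of at least one success is about 87% at correlation 0.5, 80% at 0.75 and 75% at 0.9.

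**5. All three required, each at 0.05.** Error stays at or below 5% without a split, and OSDI keeps its own 79%. The power that matters is then joint: with effect 0.5 on each scale and 62 per arm, it is 60% at correlation 0.5 and 68% at 0.8.

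**The case against.** **OSDI at 3 months is plainly intended.** OSDI alone drives the sizing, the eligibility threshold (7.1.1) and the stratification (section 6), and the objective and hypothesis are framed over 3 months. This is the natural inference, and it stands as an inference. The synopsis still gives OCI and DEQ-5 the same standing as OSDI, and no section names the visit.

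**Bonferroni already protects the error rate.** If it covers the three scales, it does, and the 8% to 14% does not arise. The rule, however, directly follows a sentence about differences between visits, so its reach across scales is not settled. If it does cover them, the stated 80% no longer describes OSDI at SD 20.

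**The trial is underpowered.** A reader might infer this from the 64% and 54%. The documents do not support it. Those figures concern OSDI under particular splits at SD 20; a smaller SD or full retention raises them, and the any-one-of-three rule with Bonferroni could keep power near 80%.

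**The stated figures hold only if OSDI at one visit is the sole primary test.** A reader might infer this too, but it is too strong. OSDI tested first in a fixed order, or all three scales required at 0.05 each, would also preserve OSDI's power and the 5% error.

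**Masking prevents selective choice.** Section 6.1.2 says "The code will be broken after completion of the study and data analysis", with an exception for participant safety. That limits choosing a result by direction of benefit. A coded A-versus-B comparison would still show which scale and visit separate the groups most.

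**Conclusion.** The concern holds as a gap in the endpoint definition, not as an error in the sample-size arithmetic. Depending on a choice the plan does not make, OSDI power at SD 20 with 62 per arm ranges from 79% (one test) through 64% (three scales) to 54% (three scales at two visits). Alternatively, OSDI keeps its 79% while familywise error at one visit is about 8% to 14%. The first set of figures rests on the plan's own difference, SD and drop-out. The second rests on assumed correlations and on an any-one-succeeds rule without adjustment.

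At least three readings reconcile the stated power and error for OSDI: sole primary at one visit, first in a fixed order, or all three required at 0.05 each. None is written down. Because the choice determines whether the trial succeeds, it has to be fixed before any A-versus-B comparison, including at an interim look.

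**What to change.** In the synopsis, 6.1.6 and 13.1.3, name one primary endpoint: the between-arm difference in OSDI at 3 months, at two-sided 0.05. The sample-size paragraph then describes the primary test. Make OCI, DEQ-5 and the 1-month results secondary, in a fixed order or a stated Bonferroni family, set before any A-versus-B comparison is run.

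Reconcile this with section 13.1: state either that no interim efficacy test of the primary endpoint will be done, or how alpha is allocated to it.

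If three primary scales are kept, state the visit and the success rule, and report the power that matches that rule:

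- **Bonferroni split across the three scales:** about 64% for OSDI at SD 20 with 62 per arm. Restoring 80% would take 86 evaluable per arm by the t-test; 86/0.9 rounds up to 96 per arm, or 192 enrolled.
- **All three must succeed:** about 60% to 68% joint power, assuming effect 0.5 on each scale and correlations of 0.5 to 0.8.

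The recommended change is wording only, with no added participants, visits or procedures. Its cost is that OCI and DEQ-5 lose primary status. Keeping all three as primary costs a less favourable power statement or a larger trial.
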